#### 573 **4.1.6 1-Week Phone Contact**

574 Study staff will perform a phone call with the participant within 7 ( $\pm 2$ ) days following Initiation  
575 of the Control-IQ study phase.

576 The following will occur:

- 577 • Assessment of compliance with study device use by review of any available device data
- 578 • Assessment of adverse events, adverse device effects, and device issues

579     • Study staff will answer any questions related to device use and follow the procedure for  
580       insulin pump optimization described above if necessary.

581           **4.1.7 2-Week Visit**

582 Participants will have a follow-up visit 14 ( $\pm 4$ ) days from the date of initiation of closed-loop  
583 system use.

584 The participant will be offered review training to address any questions on the use of the study  
585 device including meal bolus strategies and strategies related to pump use and exercise.

586 The following will occur:

587     • Assessment of compliance with study device use by review of any available device data  
588     • Assessment of adverse events, adverse device effects, and device issues  
589     • Study staff will answer any questions related to device use and follow the procedure for  
590       insulin pump optimization described above if necessary.  
591     • Download of device data (study pump, study CGM, study BG meter) as available

592           **4.1.8 4-Week Phone Contact**

593 Study staff will perform a phone call with the participant within 28 ( $\pm 4$ ) days from the date of  
594 initiation of closed-loop system use.

595 The following will occur:

596     • Assessment of compliance with study device use by review of any available device data  
597     • Assessment of adverse events, adverse device effects, and device issues  
598     • Study staff will answer any questions related to device use and follow the procedure for  
599       insulin pump optimization described above if necessary.

600           **4.1.9 6-Week Visit**

601 All participants will have a final visit within 42 ( $\pm 4$ ) days from the date of initiation of closed-loop  
602 system use, during which the following will occur:

603     • Completion of questionnaires  
604     • Collection of exercise logbook  
605     • Weight and height measurements will be repeated  
606     • Assessment of adverse events, adverse device effects, and device issues  

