607     • Download of device data (study pump, study CGM, study BG meter) as available  
608     • Study staff will supervise the participant's transition back to their prior therapy  
609       ○ Study staff will re-evaluate the subject's baseline therapy doses, noting changes in  
610        basal rates, carbohydrate ratios, and correction factors in use at the end of the  
611        trial.  
612       ○ For those subjects using basal insulin, doses will be adjusted to best match the

613 current daily insulin requirements from CSII use, typically = (total daily dose +  
614 20%)/2, with further modification as per clinical site usual practice.

615 ○ Study staff will confirm subjects have carbohydrates on hand for their drive back  
616 home, and instruct subjects to check their glucose levels when they arrive at  
617 home, prior to bedtime, and at least one time overnight on the first night to  
618 monitor for hypoglycemia, reminding subjects that insulin on board can be active  
619 for the next few hours even after stopping their pump.

620 **4.1.10 3-Day Post-Study Call**

621 All participants will have a post-study phone call 3 ( $\pm 1$ ) days after the date of their 6-Week visit  
622 and transition back to their prior insulin therapy, during which the following will occur:

623 • Check on transition back to usual home diabetes care  
624 • Assessment of adverse events

625 **4.1.11 Exercise Challenge Follow-Up**

626 Participants will be instructed to contact study staff within 24 hours of completing each exercise  
627 challenge, per guidance in section 4.1.3. The follow up call will review:

628 • The start and stop time, as well as the type of exercise performed.  
629 • Assessment of adverse events  
630 • Documentation of any safety concerns if future exercise challenges are cancelled.

631 **4.2 Early Termination Visit (If Applicable)**

632 Participants will be asked to come for an end of study visit in the event of withdrawal or early  
633 termination.

634 **4.3 Unscheduled Visits**

635 Participants may have unscheduled visits during the study period if required for additional device  
636 training or other unanticipated needs per the study investigator discretion.

637

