955 serious adverse event and/or an unanticipated adverse device effect.

956 **7.2.9 Outcome of Adverse Events**

957 The outcome of each reportable adverse event will be classified by the investigator as follows:

958 • RECOVERED/RESOLVED – The participant recovered from the AE/SAE without sequelae.  
959 Record the AE/SAE stop date.

960 • RECOVERED/RESOLVED WITH SEQUELAE – The event persisted and had stabilized  
961 without change in the event anticipated. Record the AE/SAE stop date.

962 • FATAL – A fatal outcome is defined as the SAE that resulted in death. Only the event that  
963 was the cause of death should be reported as fatal. AEs/SAEs that were ongoing at the time  
964 of death; however, were not the cause of death, will be recorded as “resolved” at the time of  
965 death.

966 • NOT RECOVERED/NOT RESOLVED (ONGOING) – An ongoing AE/SAE is defined as  
967 the event was ongoing with an undetermined outcome.

968       ◆ An ongoing outcome will require follow-up by the site in order to determine the final  
969        outcome of the AE/SAE.

970       ◆ The outcome of an ongoing event at the time of death that was not the cause of death,  
971        will be updated and recorded as “resolved” with the date of death recorded as the stop  
972        date.

973       • UNKNOWN – An unknown outcome is defined as an inability to access the participant or  
974        the participant’s records to determine the outcome (for example, a participant that was lost to  
975        follow-up).

976       If any reported adverse events are ongoing when a participant completes the study (or  
977       withdraws), adverse events classified as UADEs or related SAEs will be followed until they are  
978       either resolved, or have no prospect of improvement or change, even after the participant has  
979       completed all applicable study visits/contacts. For all other adverse events, data collection will  
980       end at the time the participant completes the study. Note: participants should continue to receive  
981       appropriate medical care for an adverse event after their participation in the study ends.

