#### **9.4.3 Safety Endpoints**

1208       • Severe hypoglycemia (needing assistance)  
1209       • DKA  
1210       • Hyperosmolar Hyperglycemic Syndrome  
1211       • Serious Adverse Events  
1212       • Unanticipated adverse device effects

1213

1215 **9.5 Analysis Datasets and Sensitivity Analyses**

1216 This is not a randomized trial so intent-to-treat does not apply. The primary analysis will be  
1217 limited to participants with at least 168 hours of CGM data during the 6-week CLC use period.

1218  
1219 A per-protocol analysis will be limited to participants who used the CLC for at least 80% of the  
1220 time during the 6-week period. If fewer than 10% of the study participants would be excluded  
1221 based on this criterion, then the per-protocol analysis will not be performed.

1222  
1223 Safety analyses will include all participants.

1224 **9.6 Analysis of the Primary Efficacy Endpoint(s)**

1225 Summary statistics appropriate to the distribution (e.g., mean and standard deviation, or median  
1226 and quartiles) will be for each of the primary efficacy endpoints (CGM-measured percentage  
1227 below 54 mg/dl and percentage above 180 mg/dl) at baseline, during CLC use, and for the  
1228 change values. Scatterplots and boxplots will be constructed to show the distribution of values at  
1229 baseline and during CLC use.

1230

1231 A pre- and post-CLC comparison will be performed using a paired t-test for each metric. If the  
1232 paired differences (i.e., change values) do not follow an approximate normal distribution, then a  
1233 non-parametric comparison based on ranks will be performed.

1234

1235 **9.7 Analysis of the Secondary Endpoint**

1236 Analysis of secondary endpoints will parallel the analysis described above for the primary  
1237 endpoints over 24 hours, daytime, and nighttime. For the post-prandial CGM metrics (4 hour  
1238 peak and AUC) and during exercise challenges, there will be no corresponding pre-study  
1239 baseline. Descriptive analyses of these metrics will be limited to values during CLC use.

1240 **9.8 Safety Analyses**

1241 All participants will be included in the safety analyses. All adverse events will be tabulated with  
1242 separate lists for events that occur before, during OL, and during CLC use.

1243  
1244 Additionally, the number of events and the event rate per 100 person-years during CLC use will  
1245 be calculated for each of the safety outcomes listed above:

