303 Impact, Diabetes Impact, PROMISE Sleep, and System Usability total or subscale scores - a paired t-test  
304 or equivalent non-parametric test will be calculated as mentioned above for the primary outcomes.

305

306 **8. Safety Analyses**

307 All enrolled participants will be included in these analyses and all their safety events up to the final visit  
308 will be reported.

310 The circumstances of all reportable cases of the following will be summarized and tabulated by study  
311 period (run-in, OL, CLC):

312     

- Severe hypoglycemia (needing assistance)
- DKA
- Hyperosmolar Hyperglycemic Syndrome
- Serious Adverse Events
- Unanticipated adverse device effects
- Ketone events defined as a calendar day with ketone level  $>1.0$  mmol/L

313

314

315

316

317

318

319 Additionally, the number of events and the event rate per 100 person-years during CLC use will be  
320 calculated for each of the safety outcomes listed above.

321

322 **9. Device Issues**

323

324 The following tabulations and analyses will be performed to assess device issues:

325     

- Device malfunctions requiring study team contact and other reported device issues.
- Rate of different failure events and alarms per 24 hours recorded by the Control-IQ system –  
326       overall and by study week.

327

328

329

330 **10. Protocol Adherence and Retention**

331

332 The following measures of adherence will be tabulated during the 2-4 weeks of OL and during the 6  
333 weeks CLC follow-up periods:

334

- 335 • Number of protocol and procedural deviations
- 336 • Flow chart accounting for all enrolled participants up to end of study
- 337 • Flow chart of all enrolled participants at all scheduled visits and phone contacts post treatment  
initiation
- 338 • Number of and reasons for unscheduled visits and phone calls
- 339 • Number of participants who stopped OL or CLC use and reasons

340

341 **11. Intervention Adherence**

342

343 Descriptive summary statistics will be given for the percentage of time that the CLC is in active mode  
344 and the amount of CGM use over the 6-week CLC use period. A scatterplot of these two percentages  
345 will be constructed.

346

Boxplots will be given for each of these percentages for each one of the 6 weeks of follow-up.

347

Descriptive statistics will be given for the percentage of time spent in each of the CLC operational  
348 modes.

349

350 **12. Baseline Descriptive Statistics**

351

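### SAP section 8 stops safety reporting at the 6-week visit, before the Protocol's last adverse event assessment, and events after the device comes off have no clear reporting period

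*SAP*

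**What the plan says.** **Cut-off.** SAP section 8 states "All enrolled participants will be included in these analyses and all their safety events up to the final visit" will be reported. Protocol 4.1.9 fixes the term: "All participants will have a final visit within 42" (±4) days of starting closed loop. SAP 4.8 also calls the 6-week visit the final visit. SAP 5.2, which defines the safety cohort, takes safety data to the end of the study instead.

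**Collection after that visit.** Protocol 4.1.10 schedules a call 3 (±1) days after the 6-week visit "and transition back to their prior insulin therapy, during which the following will occur". One of the two items listed is an adverse event assessment. The schedule tables (Protocol Table 1, SAP Table 2) mark adverse event assessment in the +3d column.

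**Tabulation.** Protocol 9.8 says "All adverse events will be tabulated with" "separate lists for events that occur before, during OL, and during CLC use". SAP 5.2 names run-in, open loop (OL) and closed-loop control (CLC) use. SAP 8 names run-in, OL and CLC. Both documents add an event rate per 100 person-years during CLC use.

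**Risk at the transition.** At the 6-week visit, Protocol 4.1.9 returns participants to their prior therapy. For those who use basal insulin, the dose is matched to "current daily insulin requirements from CSII use, typically = (total daily dose" plus 20%), divided by 2. All are told to check glucose on arriving "home, prior to bedtime, and at least one time overnight on the first night to" watch for hypoglycemia, because insulin from the pump may still be acting.

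**The concern.** Safety is the first stated objective, and severe hypoglycemia, diabetic ketoacidosis and hyperosmolar hyperglycemic syndrome are key safety endpoints. A programmer who follows SAP 8 would close the safety tables at the 6-week visit and leave out anything first reported at the post-study call. Those data are already collected, and Protocol 9.8 says they will be tabulated. The omitted days are also the ones in which the Protocol asks participants to look out for low glucose.

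The second gap concerns classification. Two kinds of event occur when the participant is off the device: those after removal at 6 weeks, and those in someone who stops early but stays in the study, as Protocol 7.6.1 encourages. The second kind falls before the final visit, so it would be reported, but under no clearly applicable period. If either kind is filed under CLC and carried into the rate, that rate counts events that did not occur during device use. The study is meant to inform a larger trial, so both the completeness of the tables and the meaning of the rate matter.

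**Working it through.** The plan states no figure to reproduce: N=30 is a convenience sample, and no safety event rate is given. The check is a comparison of text, then person-time arithmetic for scale.

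**Step 1: the limits side by side.**

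| Place | Limit or period |
|---|---|
| SAP 8 | final visit |
| SAP 4.8, Protocol 4.1.9 | final visit = 6-week visit |
| SAP 5.2 | end of the study |
| SAP 4.3 | end of study visit = visit closing the 6-week CGM window |
| Protocol 4.1.10, schedule tables | adverse events assessed 3 (±1) days later |
| Protocol 9.8 | all adverse events; lists for before, OL, CLC use |
| SAP 5.2, SAP 8 | run-in, OL, CLC (5.2: CLC use) |

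The SAP 8 limit falls before the last scheduled assessment. The SAP 5.2 limit may or may not include it.

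**Step 2: person-time between the 6-week visit and the call.** Inputs: n = 30 planned starters or 24 completers (Protocol 9.3, SAP 3) and d = 2, 3 or 4 days (Protocol 4.1.10). Formula: n × d / 365.25.

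- n = 30: 30 × 3 / 365.25 = 0.246 person-years (0.164 for 2 days, 0.329 for 4).
- n = 24: 24 × 3 / 365.25 = 0.197 person-years (0.131 to 0.263).
- Relative to 42 closed-loop days: 3/42 = 7.1% (2/42 = 4.8%; 4/42 = 9.5%).

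**Step 3: effect of one misplaced event on the CLC rate.** Closed-loop person-time is n × 42 / 365.25, and one event adds 100 divided by that person-time.

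- n = 30: 30 × 42 / 365.25 = 3.45 person-years; 100 / 3.45 = 29.0 per 100 person-years.
- n = 24: 24 × 42 / 365.25 = 2.76 person-years; 100 / 2.76 = 36.2 per 100 person-years.
- If the 3 post-removal days also entered the denominator at n = 30: 100 / (30 × 45 / 365.25) = 27.1 per 100 person-years. Widening the denominator hardly reduces the effect.

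**Step 4: how likely an event is in the window.** The documents give no rate, so these are assumptions. With 0.246 person-years and a Poisson count, the chance of at least one event is 1 − exp(−rate × 0.246). It is 2.4%, 6.0% and 11.6% at assumed rates of 10, 25 and 50 per 100 person-years.

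**The case against.** The strongest reply is that the SAP does not clearly exclude the call. SAP 5.2 defines the safety cohort and takes data to the end of the study, and the SAP's own schedule marks adverse event assessment at +3d. The places where the SAP uses *end of study* for the 6-week visit (4.3 and 7.3) concern CGM and weight, not safety. This has force. A reader might infer that both SAP limits plainly shut out the call, but the documents support less: SAP 8 does so as written, and SAP 5.2 is open. What stands is that the two sections set different limits for the same tables, and the more specific one falls too early.

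A reader might also infer that no period could hold a post-removal event. That goes too far. Protocol Table 2 is titled as the Control-IQ phase schedule and lists the post-study contact, so by phase such an event could be filed under CLC. But SAP 5.2 and Protocol 9.8 speak of CLC *use*, which had ended. Filing by phase also invites the event into a rate defined on use. The placement is therefore unclear, and a separate category resolves it.

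Third, no one would miss such an event during the study. Under Protocol 7.5 the Medical Monitor reviews every reported adverse event. This is correct, and the point is limited to the planned tables.

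Last, Protocol 7.2.9 might be cited as tying the end of collection to the last contact. Its reference to visits and contacts belongs to the sentence on following unanticipated device effects and related serious events after completion, so it is not relied on here.

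**Conclusion.** The point holds as a minor one. SAP 8 applied as written omits adverse events that the Protocol collects at the post-study call and says it will tabulate, and SAP 5.2 does not clearly restore them. Separately, the listed periods do not say where events off the device belong.

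The omitted window is about 0.25 person-years at n = 30 (0.16 to 0.33 over the call's window), assuming all 30 starters reach the 6-week visit. An event in it is unlikely at the assumed rates. One off-device event placed in the CLC rate would raise it by about 29 per 100 person-years at n = 30, or 36 at n = 24, assuming 42 days of closed loop each.

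The documents do not support reading this as a failure of safety oversight, since Medical Monitor review is unaffected. The CGM efficacy analyses have their own windows and do not change.

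**What to change.** 1. In SAP 5.2 and SAP 8, replace both cut-offs with one: *through the 3-day post-study call*.
2. In SAP 5.2, SAP 8 and Protocol 9.8, add an *after closed-loop* category. It should cover events after removal at the 6-week visit and events in participants who stop the device early but remain in the study. State that these events do not enter the rate during CLC use.

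The cost is one aligned phrase, one extra table category and one sentence on the rate. No new data are needed, because adverse events are already assessed at the call.
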